1.2 List of abbreviations

AE	Adverse Event
AR	Adverse Reaction
ARDS	Acute respiratory distress syndrome
BAC	Best Available Care
BID	Twice per day
СА	Competent Authority
CF	Cystic Fibrosis
cfDNA	Cell-free DNA
CI	Chief Investigator
Conmeds	Concomitant medications
CoV	Coronavirus
CRF	Case Report Form
CRO	Contract Research Organisation
CRP	C-reactive protein
СТ	Computer tomography
СТА	Clinical Trial Authorisation
СТІМР	Clinical Trial of Investigational Medicinal Product
DI	Designated Individual
DMC	Data Monitoring Committee
DNA	Deoxyribonucleic acid
DNase	Deoxyribonuclease
DSUR	Development Safety Update Report
EC	European Commission
EMA	European Medicines Agency
EU	European Union
EUCTD	European Clinical Trials Directive
EudraCT	European Clinical Trials Database
EudraVigilance	European database for Pharmacovigilance
FDA	Federal drug administration
FVC	Forced vital capacity
GAfREC	Governance Arrangements for NHS Research Ethics

GCP	Good Clinical Practice
GMP	Good Manufacturing Practice
H3	Histone 3
HTA	Human Tissue Authority
ICF	Informed Consent Form
ICU	Intensive care unit
IL-1 β	Interleukin -1 beta
IL-6	Interleukin-6
IL-8	Interleukin-8
ISARIC	International Severe Acute Respiratory and Emerging Infection Consortium
ISF	Investigator Site File
ISRCTN	International Standard Randomised
MA	Marketing Authorisation
MHRA	Medicines and Healthcare products Regulatory Agency
MPO	Myeloperoxidase
MS	Member State
MV	Mechanical Ventilation
NIHR	National Institute for health research
NHS R&D	National Health Service Research & Development
NETs	Neutrophil extracellular traps
NOCRI	NIHR Office for Clinical Research Infrastructure
PCR	Polymerase chain reaction
РСТ	ProCalcitonin
PD	Pharmacodynamics
PI	Principal Investigator
РО	Purchase order
PIS	Participant Information Sheet
PL	Product License
QD	Once per day
QA	Quality Assurance
QC	Quality Control

RECOVERY	Randomised evaluation of COVID-19 therapy
RCT	Randomised Controlled Trial
REC	Research Ethics Committee
RSI	Reference Safety Information
SAP	Statistical Analysis Plan
SAR	Serious Adverse Reaction
SAE	Serious Adverse Event
SDV	Source Document Verification
SOFA	Sepsis-related Organ Failure Assessment
SOP	Standard Operating Procedure
SMPC	Summary of Product Characteristics
SUSAR	Suspected Unexpected Serious Adverse Reaction
ΤΝFα	Tumour necrosis factor alpha
TRC	Translational Research Collaboration
UCL	University College London
UCLH	University College London hospital
WHO	World health organisation

This study proposes to treat hospitalised subjects with COVID-19 by administration of 2.5mg Dornase alfa BID for 7 days. The effect on NETs, inflammation and clinical course will be closely monitored. We expect to see a reduction in circulating NETS and inflammatory biomarkers that will result in clinical benefit. Historic controls will be derived from an existing database of 120 subjects with COVID-19 that have been admitted to UCL since the beginning of the outbreak.

It is worth noting that dornase alfa can be self-administered at home. Therefore, dornase alfa has the potential to provide benefit in subjects with COVID-19 who have mild disease and are self-isolating and in those discharged from hospital to recuperate at home.

Objectives:	Primary objective : to assess the effect of nebulised dornase alfa on C-reactive Protein (CRP) in hospitalised participants with COVID-19.
	Secondary objective : to assess the effect of nebulised dornase alfa on clinical responses in hospitalised participants with COVID-19.
	Exploratory objective : to assess the effect of nebulised dornase alfa on inflammation, biomarkers of NETs, coagulation, complement activation and haemolysis in hospitalised participants with COVID-19.
Type of trial:	A single-site, randomised, controlled, parallel design, open-label trial of an approved nebulised recombinant human DNase enzyme (dornase alfa) to reduce hyperinflammation in hospitalised participants with COVID-19 (The COVASE Trial).
Trial design and methods:	An open-label, randomised, Best-Available-Care (BAC) and historic-controlled trial of nebulised dornase alfa [2.5 mg BID] for 7 days in participants with COVID-19 who are admitted to hospital and are at risk of ventilatory failure (the COVASE study). Controls will include a randomised arm to receive BAC, historic data from UCLH patients with COVID-19 and biobanked samples will be used to demonstrate an effect of dornase alfa. CRP will be measured to assess the effect of dornase alfa on inflammation. Clinical endpoints and biomarkers (e.g. d-dimer) will be used to assess the clinical response. Exploratory endpoints will explore the effects of dornase alfa on features of neutrophil extracellular traps (NETs).
Trial duration per participant:	Six weeks from consent to last trial assessment.
Estimated total trial duration:	Four - five months from when first participant enrolled to last participant follow-up.
Planned trial sites:	Single site
Total number of participants planned:	40 participants will be enrolled. A sample size re-estimation is planned to occur approximately one third of the way through the study (e.g. when 12 participants have been randomised). At this point, the decision may be made to randomise additional participants if the variability of the primary endpoint is higher than anticipated.
Main inclusion/exclusion criteria:	Participants who are hospitalised for COVID-19 will be recruited into the study.

Inclusion criteria:

- 1. Male and female participants, aged \geq 18 years.
- Participants who are hospitalised for suspected Coronavirus (SARS-CoV)-2 infection confirmed by polymerase chain reaction (PCR) test or radiological confirmation with chest CT scan
- Participants with stable oxygen saturation (>=94%) on supplementary oxygen
- 4. CRP >= 30 mg/L.
- Participants will have given their written informed consent to participate in the study and are able to comply with instructions and nebuliser.

Exclusion criteria

- Females who are pregnant, planning pregnancy or breastfeeding.
- Concurrent and/or recent involvement in other research or use of another experimental investigational medicinal product that is likely to interfere with the study medication within the last 3 months before study enrolment.
- 3. Serious condition meeting one of the following:
 - respiratory distress with respiratory rate >=40 breaths/min
 - II. oxygen saturation <=93% on high-flow oxygen
- 4. Require mechanical invasive or non-invasive ventilation at screening
- Concurrent severe respiratory disease such as asthma, COPD and/or ILD.
- Any major disorder that in the opinion of the Investigator would interfere with the evaluation of the results or constitute a health risk for the study participant.
- Terminal disease and life expectancy <12 months without COVID-19.
- 8. Known allergies to the dornase alfa and excipients.
- 9. Participants who are unable to inhale or exhale orally throughout the entire nebulisation period.

Statistical methodologyFull details of the planned statistical analysis will be presented in
the Statistical Analysis Plan (SAP). All baseline data,
demographics, endpoints, safety and tolerability will be
summarised overall and by treatment group and by day. In
general, continuous data will be summarised using the mean
(standard deviation), median (1st and 3rd quartiles), minimum

and maximum, and categorical data will be represented as frequency counts (percentages).

For analyses relating to the primary objective, group comparisons will be performed using a repeated measures mixed model, adjusted for baseline factors and with treatment as the main effect. Prior to analysis, all endpoints will be assessed for conformance to normality assumptions and the appropriate transformation will be conducted if necessary. Some exploratory endpoints may only be available in the active treatment group. In this case, a within group analysis will be conducted to compare baseline and post-baseline measurements.

An interim analysis will be conducted when 12 participants have been randomised. The results of the interim analysis will be used to re-estimate the sample size if necessary.

3 Background and rationale

Clinical background

COVID-19 is a heterogeneous disease caused by infection with SARS-CoV-2 and although the majority of patients (80%) have mild disease, 15% will require oxygen and of these 25% will require ICU, of which 47 – 71% require ventilatory support. Risk factors for severe disease include older age, male sex, obesity and comorbid disease. There are no specific cures for COVID-19 and current care is supportive. A key challenge is to intercept patients early in the course of their disease to prevent deterioration and reduce the numbers that need ventilatory support, a life-saving treatment that is currently only available for a minority of patients.

SARS-CoV-2 is able to directly infect nasal, bronchiolar and alveolar epithelial cells resulting in lung inflammation, characterised, in severe cases, by an over-exuberant inflammatory response, shortness of breath and hypoxaemia. Once SARS-CoV-2 infection progresses to the stage of pneumonia, key pathogenic drivers result in symptoms characteristic of the acute respiratory distress syndrome (ARDS) with a high mortality.

In patients with confirmed COVID-19 pneumonia, 50% developed dyspnoea at 8 days after illness onset (range: 5–13 days). Mortality of these patients is around 4-15%, as a result of ARDS, coagulation dysfunction, and secondary infection that may result in septic shock and multi-organ failure (Zhou et al., Lancet 2020). Cytokines are thought to be key drivers of these pathological events and in particular levels of IL-6 are found to be raised in COVID-19 patients and to correlate with mortality (Gong et al., medRxiv 2020). Anti-IL-6 is seen as a potential therapy in COVID-19 following favourable reports from a clinical study in China.

There is an urgent need to intervene and reduce the inflammatory response of patients with COVID-19 early in the course of their disease and so prevent progression to ICU.

Scientific background

Our hypothesis is that in the COVID-19 lung, the release of neutrophil extracellular traps (NETs) by neutrophils promotes lung damage and the induction of pathogenic pro-inflammatory cytokines, such as IL-6 and IL-1. This inflammatory cascade recruits additional neutrophils leading to a pathogenic feedback amplification loop. High neutrophil infiltration is prominent in the lungs of COVID-19 patients and evidence of NET components in the circulation and lung biopsies has been reported in clinical study of COVID-19 patients (Betsy J. Barnes et al., JEM 2020l; Zuo et al. medRxiv preprint doi:https://doi.org/10.1101/2020.04.09.20059626). Based on this evidence, blocking or clearing NETs to treat severe COVID-19 symptoms has now been proposed by an international consortium (Betsy J. Barnes et al., JEM 2020).

NETs are composed of a backbone of decondensed chromatin fibres coated with antimicrobial granular and cytoplasmic proteins, such as myeloperoxidase, neutrophil elastase (NE) and α - defensins. Doublestranded DNA is a major component of NETs, which prevents their degradation. This extracellular DNA is normally broken down by endogenous deoxyribonucleases (DNases) but in severe inflammation these DNases may become overwhelmed by a massive release of NETs and are unable to completely degrade NETs. Our recent work suggest incomplete NET degradation would lead to amplification rather than reduction of inflammation.

While sensing of microbes and viruses promotes inflammation, the release of endogenous host molecules during infection, known as damage-associated molecular patterns (DAMPs), can amplify cytokine induction. Work in [name] lab at the Francis Crick institute has identified specific DAMPs that are critical for the induction of pathogenic hyperinflammation during infection. Free circulating histones are key pathogenic factors in microbial sepsis. We recently found that extracellular chromatin acts as a potent pro-inflammatory signal, allowing extracellular chromatin structures called neutrophil extracellular traps (NETs) to induce IL-1 β and IL-6, via Toll-like receptor 4 (TLR4) (Tsourouktsoglou et al. *in press*).

Consistently, NET-mediated pathology causes death in murine models of severe pulmonary *Influenza* infection (Pillai et al., Science 2016) and the presence of NETs correlates with flu severity in humans (Zhu et al., J. Infect. Dis. 2018). DNase treatment significantly delayed mortality in severe flu in immune-compromised mice (Pillai et al., Science 2016) and cleared NETs and lowered airway obstruction in severe bovine respiratory syncytial virus (RSV) infection (Cortjens et al., Thorax 2018). Finally, mice that are genetically pre-disposed to NET overproduction following pulmonary infection with a virulent fungal mutant strains can be rescued from lethality with NET formation inhibitors (Papayannopoulos, Nat. Rev. Immunol. 2018). NETs are major drivers of coagulation during sepsis, particularly in the absence of endogenous DNAses, and are regulated by the complement cascade (Jimenez-Alcazar et al., Science 2017).

Rationale for the trial

Dornase alfa is a recombinant human DNase enzyme indicated in conjunction with standard therapies for the management of cystic fibrosis (CF) to improve pulmonary function. Dornase alfa degrades extracellular DNA, and so promotes the clearance of NETs and lead to a significant improvement in lung function for treated CF patients by facilitating mucus clearance in the lung. Dornase alfa is approved worldwide as a nebulised formulation, with an excellent safety profile and is well tolerated. The most common side effect is a hoarse voice. Moreover, dornase alfa could be administered in addition to effective antiviral therapy and should not interfere with antiviral drugs that could be used for COVID-19.

By facilitating the clearance of NETs, dornase alfa not only facilitates sputum clearance in CF patients, but has additional anti-inflammatory activity. Dornase alfa has been shown to reduce NETs in the bronchoalveolar lavage (BAL) and sputum of participants with CF (Konstan et al 2012). In the Bronchoalveolar Lavage for the Evaluation of Anti-inflammatory Treatment (BEAT) study, the percentage of neutrophils in bronchoalveolar lavage fluid significantly increased in untreated CF patients (P<0.02) while remaining constant in the dornase alfa-treated group. Levels of elastase and IL-8 also significantly increased from baseline in the untreated group (P<0.007 and P<0.02 for elastase and IL-8, respectively), but remained stable in patients receiving dornase alfa (Konstan and Ratjen, J. Cyst. Fibros. 2012).

There is scientific evidence to support the potential benefits of dornase alfa in COVID-19 infection. Viral sepsis driven by a hyperinflammation is thought to be a major cause of mortality in COVID-19 infection. Interleukin-1 β (IL-1 β), IL-6 and TNF α are key cytokines in microbial sepsis. Positive outcomes with Roche's Actemra (tocilizumab), an antibody that blocks the pro-inflammatory cytokine interleukin-6 (IL-6), in COVID-19 treatment has led to several anti-inflammatory trials.

Our hypothesis is that nebulised dornase alfa will break down the DNA backbone of NETs in the COVID-19 lung which will promote the degradation of pro-inflammatory extracellular histones and prevent the amplification of the inflammatory response and the resultant lung damage.

Positive data will enable rapid testing into a large clinical trial in the UK and prevent ICU capacity issues faced today. Dornase alfa is a cost-effective drug and is currently available for prescription.

We propose to test this hypothesis with this COVASE Phase IIa trial. We propose that all people with COVID-19 who are admitted to hospital for supplementary oxygen, who showed evidence of systemic inflammation but did not immediately require intubation and ventilation, would be eligible for nebulised dornase alfa, a safe and cost-effective treatment, twice daily for 7 days.

The hypothesis to be tested is illustrated in Figure 1.

Potential Real-World evidence

It is theoretically possible that the CF population could provide Real-World evidence on the effect of dornase alfa on COVID-19. Some participants with CF may develop COVID-19 and may or may not be on dornase alfa. An epidemiological study could determine outcomes in the two groups (CF + COVID-19 not taking dornase alfa and CF + COVID-19 taking dornase alfa). However, currently, the numbers are too low. Considering participants with CF across London, there are a few adults with COVID-19, none of whom have severe disease or have been admitted to ITU. However, they are likely to have been 'shielding' since before the term was coined. So far, no paediatric cases have been reported. However, given that much of the infected paediatric age group elsewhere is asymptomatic or mild, they may not be effectively documented. Therefore, it is not possible at this stage to consider the effect of dornase alfa on the progression of COVID-19 in the setting of CF. All cases of COVID-19 infection in participants with CF will be captured through the national patient registry. This also identifies patients on dornase alfa, so retrospectively these cohorts can be assessed. Data will not be available in high enough numbers for this to be useful during the current pandemic.

Dornase alfa dosing rational

The dose to be administered in this trial is 2.5 mg dornase alfa BID (approved) administered with the eRapid nebuliser (or equivalent jet nebuliser connected to an air compressor with an adequate air flow and equipped with a mouthpiece as recommended for dornase alfa-see section 8.3 Table 1). This is twice the standard daily dose (2.5mg QD) and is recommended for older/refractory people with CF. It has been shown to be safe and well tolerated in children and adults with CF. Doses of 2.5mg QD have been

administered for years (since 1994) to thousands of people with CF. Higher doses up to 10mg BID have been used in short-term studies with a similar safety and tolerability profile. Dornase alfa has been shown to be safe and well-tolerated during acute exacerbations of CF. Dornase alfa is administered in addition to other treatments for CF (FDA label and EMA SmPC).

Thus, dornase alfa at 2.5 mg BID for seven days is expected to be safe and well-tolerated in hospitalised participants with COVID-19. It is well tolerated and has the potential to block the production of not one but several pro-inflammatory cytokines and acts enzymatically. Moreover, it has been shown not to interfere with anti-viral immune defence (Cortjens et al., Thorax 2018).

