Exploratory objective: to assess the effect of nebulised dornase alfa on inflammation, biomarkers of NETs, coagulation, complement activation and haemolysis in hospitalised participants with COVID-19

- Exploratory endpoints may be measured in the circulation (blood) and, when these are available, in bronchial secretions (spontaneous expectorant or routine bronchoscopy during MV). They may include, but are not limited to:
 - Circulating pro-inflammatory cytokines (e.g. IL-6, TNFα, IL-1β, IL-8)
 - Cell-free DNA (cfDNA)
 - Circulating histone
 - Citrullinated H3
 - NET Elisa assay
 - NET formation assay
 - Coagulation (e.g fibrin, tissue factor, Von Willebrand factor, thrombin, thromboxane A2)
 - Complement cascade (e.g C1q)
 - Haemolysis (e.g RBC lysis)
 - Expression profiling of white blood cells by RNA seq

5 Trial design

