5.1 Overall design

A single-site, randomised, controlled, parallel design, open-label investigation of an approved nebulised recombinant human DNase enzyme (dornase alfa) to reduce hyperinflammation in hospitalised participants with COVID-19 (the COVASE Trial: Figure 2).

Figure 2: COVASE Trial Schematic

Participants will be screened, consented, enrolled and randomised up to 3 days after they are admitted to the hospital. They will be randomised in a 3:1 ratio to receive BAC + dornase alfa or

BAC alone. A total of 40 participants will be enrolled (30 to receive BAC plus dornase alfa and 10 to receive BAC). On Day1 to Day7 of the trial, participants randomised to the active arm, will receive 2.5mg BID nebulised dornase alfa in addition to BAC. On Day1, Day3, Day5 and Day7, blood samples will be drawn in both trial arms in order to test pharmacodynamic endpoints (PD), biomarkers and clin labs. Clinical assessments will be undertaken daily (as per UCLH clinical guidelines). Participants will be followed until discharge or death or a maximum of 28 days follow-up.

A sample size re-estimation is planned when 12 participants have been randomised. This analysis will ensure that the assumptions made in the sample size calculation remain valid. However, if the variability is higher than expected then up to an additional 10 participants will be enrolled and treated with dornase alfa (up to 50 participants in total).

CRP has been chosen as the Primary Endpoint because it is a clinically important marker of inflammation and is used to make clinical treatment decisions. In addition, it is induced by the over-exuberant inflammation mediated by the NETs and inflammatory histones. CRP is a prognostic marker and correlates with clinical symptoms and response to therapy. Thus, CRP is at the centre of the COVID-19 disease pathway: from NETS to CRP to clinical disease progression.

Based on clinical judgement, it may be decided to keep some participants on treatment for up to 14 days. In particular, if participants have significant benefits from therapy, but show relapses of the COVID-19 inflammatory state (rising CRP and increasing oxygen requirements in the absence of bacterial infection), on completing 7 days of treatment, then the medical team have the choice of reinstating dornase alfa treatment for up to 7 further days (14 days in total). Blood sampling, as specified, will continue until the last day of dosing with dornase alfa.

Study controls

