Due to the evolving situation with hospitalised COVID-19 participants, the burden on the NHS and the availability of other COVID-19 trials, it is considered inappropriate to conduct a placebocontrolled study. Therefore, a randomised, controlled, open-label approach where dornase alfa is administered on top of BAC and compared to BAC alone has been adopted.

The data derived from the 10 participants who are randomised to the BAC arm of the study who do not receive dornase alfa will provide control data for all of the study endpoints.

The 30 participants randomized to BAC + dornase alfa will be compared to 10 randomised controls from the COVASE study. In addition, 10 participants in other clinical trials on BAC (biobanked samples) and 60 participants from a historic database of the first 120 people with COVID-19 treated at UCLH will also be used as comparator data.

However, to enhance the control group, a hybrid approach will be applied such that additional data will be combined with the randomised controls, illustrated in Figure 3. The sample size calculation indicates that 90 evaluable participants are required (60 control:30 active). These control data may include: data from the randomised BAC arm, historic COVID-19 UCLH database, biobanked samples from other ongoing trials and observational trials in COVID-19.

This hybrid strategy allows two things:

- provides comparators for all of the study objectives (including limited data for the exploratory objectives)
- demonstrates that the historic controls are representative/similar to the study population

Comparator data from UCLH is available as historic controls for the Primary and Secondary Endpoints. A database of the first 120 participants with COVID-19 admitted to UCLH is available and being analysed currently. CRP is routinely measured daily (or on alternate days) in all participants admitted to UCLH and will be used to control for the Primary Endpoint. All of the Secondary Endpoints are also routinely measured and will be available in the database. Participants in the database will be selected to act as controls as follows:

- 1. Apply the inclusion and exclusion criteria of the COVASE study
- 2. Additional selection to identify closest matches using a propensity score based on age, gender, BMI, baseline CRP, oxygen requirements and the number of comorbidities.

At least 60 control participants are expected to be available to act as controls.

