11.2 Sample size and recruitment

11.2.1 Sample size calculation

Sample size calculations were produced using the proc power function in SAS Version 9.4. These were conducted to achieve 80% power to detect difference in the active arm versus the control group at the 5% level of significance. Based on a mean of 99mg/L in the control group and a common standard deviation of 62mg/L derived from the literature (Han et al., 2020; Zhou, 2020), a total sample size of 90 participants would provide sufficient power to detect a greater than a 40% relative difference for CRP in the dornase alfa group compared to the control group. Given the reported average values in severe and non-severe participants and on clinical observations from COVID-19 patients, this difference would be achievable and clinically relevant.

This study will use existing data collected at UCLH from participants admitted with COVID-19 as a comparator group. Participants in the database will be selected to act as controls as follows:

- Apply the inclusion and exclusion criteria of the COVASE study
- Additional selection to identify closest matches

This will give the correct ratio of active versus comparator (ratio of 1:2). To achieve the required power, this would result in 30 participants in the active treatment group and at least 60 in the control. An additional 10 participants will be recruited as a control for the exploratory objectives and to compare the characteristics of enrolled participants with the historical controls. This gives a total of 40 participants enrolled in the study and 60 historical controls.

Participants who drop out of the study will be replaced so the sample size relates to the number of evaluable participants required.

A re-estimation of the sample size will be carried following an interim analysis when 12 participants have been randomised.

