11.3 Statistical analysis plan

11.3.1 Summary of baseline data and flow of participants

All subjects enrolled in the study will be accounted for in a CONSORT diagram. There will be multiple analysis populations:

1 Primary analysis population - all evaluable patients randomised to dornase alfa + matched historical comparators.

2 Per protocol population - as above but excluding protocol violations.

3 Safety population - all enrolled patients receiving at least one dose of dornase alfa and the comparator groups.

4 Comparator population - the matched historical controls, patients randomised to BAC and historical records linked to biobanked samples.

5 Exploratory analysis population - all evaluable patients randomised to dornase alfa or to BAC plus historical patient data from biobanked samples.

The primary analysis will be conducted using the primary analysis population and is based on the ITT principle. Details on subjects enrolled but not included in the analysis populations will be presented as part of the CONSORT diagram.

The key baseline data that will be used to compare the groups and the analysis populations are age, gender, BMI, baseline CRP, oxygen requirements and the number of comorbidities. In general, continuous data will be summarised using the mean, standard deviation, median, minimum and maximum and categorical data will be represented as frequency counts and percentages.

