11.3.4 Sensitivity and other planned analyses

All primary and secondary analyses will be repeated using the primary analysis population and the per protocol population. The use of the per protocol population is only as a sensitivity analysis to understand the impact of non-compliance.

This study utilises a combination of enrolled and randomised participants, historical controls and banked biosamples. Descriptive statistics will be produced for key baseline variables for all data sources within the comparator population. These will be used to evaluate the comparability of the source data.

There are planned subgroup analyses that relate to secondary objectives. A comparison of the secondary endpoint, time on MV, between treatment groups will be conducted only in participants that received MV. Other subgroup analyses may be performed but these are considered to be exploratory.

Further exploratory analyses are planned for the exploratory endpoints in the study. These analyses will follow the same principles and considerations with regards to the application of statistical approaches for specific data types and data structures. The exploratory analyses will use the exploratory analysis population.

Full details of the planned statistical analysis will be presented in a separate Statistical Analysis Plan (SAP). This will be finalised prior to database lock. The results from all analyses will be presented in the form of tables, figures and listings.

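### The protocol summary's before-after analysis of exploratory endpoints seen only in the dornase alfa arm cannot show a drug effect and conflicts with the BAC control planned elsewhere (minor)

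*Protocol*

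**What the plan says.** The exploratory objective (Protocol section 4) is causal: "to assess the effect of nebulised dornase alfa on inflammation, biomarkers of NETs, coagulation, complement activation and haemolysis". For its analysis, the Statistical methodology part of the Protocol summary (section 2) says: "Some exploratory endpoints may only be available in the active treatment group". It continues: "In this case, a within group analysis will be conducted to compare baseline and post-baseline measurements".

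Other places provide a concurrent control:

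- Protocol 5.1, overall design: on Days 1, 3, 5 and 7, "blood samples will be drawn in both trial arms in order to test pharmacodynamic endpoints (PD), biomarkers and clin labs".
- Protocol 5.1, Study controls: data from the 10 randomised BAC participants "will provide control data for all of the study endpoints".
- Protocol 11.2.1: "An additional 10 participants will be recruited as a control for the exploratory objectives".
- Protocol 11.3.1: the exploratory population is "all evaluable patients randomised to dornase alfa or to BAC plus historical patient data from biobanked samples". SAP 6.5 agrees.
- Protocol 11.3.4: "The exploratory analyses will use the exploratory analysis population".
- SAP 2.3.3: the exploratory null hypothesis is no difference between dornase alfa plus BAC and BAC only.

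SAP 11.3 leaves the exploratory analyses to be done separately. The SAP therefore neither repeats nor withdraws the rule in the summary.

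**The concern.** Participants enter while acutely inflamed (CRP of at least 30 mg/L, Protocol 7.1.1) and all receive best available care. Protocol 6.5 accepts that other medication given as BAC may move the endpoints, for example by lowering CRP. A change from baseline in the treated arm alone therefore mixes any drug effect with the course of the illness, the background treatment and, for markers correlated with CRP, regression to the mean.

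These endpoints carry the mechanistic argument of the trial. The summary expects circulating NETs and inflammatory biomarkers to fall, so a fall that happened without the drug would look like confirmation. A natural rise would have the opposite result and could hide a real effect.

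**Working it through.** **1. Where could one-arm data arise?**

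| Material | Same samples in randomised BAC? | Source |
|---|---|---|
| Blood for PD and biomarkers: screening, Days 1, 3, 5, 7, final visit | Yes. The blood-volume table gives 6 draws both for BAC and for 7-day dornase alfa | Protocol 5.1, 8.5, Appendix 1 |
| Blood on Days 9, 11, 14 | No. Drawn only under extended dosing (9 draws in total) | Protocol 8.5, Appendix 1 note 10 |
| Bronchial secretions | Not assured. Collected only for clinical reasons | Appendix 1 note 7 |

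For blood at the shared visits, the condition in the summary is met only if BAC samples are not assayed. No section plans that, but none commits to assaying them either. The Day 9, 11 and 14 draws have a further problem: Protocol 8.3.1 gives rising CRP after Day 7 as the leading reason for extension, so these patients are partly selected on a high value.

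**2. The plan's own figure.** The only sample size calculation is for CRP: mean 99 mg/L, SD 62 mg/L, 40% relative difference, 30 against 60. The difference is 0.40 × 99 = 39.6 mg/L, or 39.6/62 = 0.64 SD. The noncentrality is 0.64/√(1/30 + 1/60) = 2.86, and the two-sided 5% t-test has power 0.807. The stated 80% at N = 90 is reproduced. No fall, SD or sample size is given for any exploratory marker.

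**3. Illustrative error rate of a before-after test.** Assumptions, none of them from the documents: no drug effect, a natural fall f of 20% or 30%, an SD s of the log change of 0.5 or 0.8, and a two-sided 5% paired t-test. The noncentrality is −ln(1 − f)/s × √n. Example: f = 0.20, s = 0.5, n = 30 gives 0.223/0.5 × 5.477 = 2.44.

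| Pairs | s = 0.5, f = 20% | s = 0.5, f = 30% | s = 0.8, f = 20% | s = 0.8, f = 30% |
|---|---|---|---|---|
| 30 | 0.66 | 0.97 | 0.31 | 0.66 |
| 8 | 0.20 | 0.41 | 0.11 | 0.19 |
| 5 | 0.12 | 0.24 | 0.08 | 0.12 |

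Thirty pairs corresponds to a blood marker assayed in the active arm only. Five to eight is an assumed count for bronchial samples.

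**4. The randomised comparison under the same problem.** With drift of 0.25, 0.5 or 0.75 SD in both arms, baseline-to-follow-up correlation 0.5 and no drug effect (20,000 simulated trials each), the 30 against 10 comparison of change was significant in 4.9-5.2% of trials. The one-arm test was significant in 27%, 75% and 98%.

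**5. The price of the control.** At 30 against 10, 80% power needs a difference of about 1.05 SD. Power at 0.64 SD is about 40%.

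**The case against.** The strongest reply is that the controlled analysis is already the plan. The summary's rule is conditional and stands only in the summary. The protocol body and the SAP both set up a comparison with BAC, and blood is scheduled in both arms, so for circulating markers the condition should not arise. This stands, and it is why the point is one of reconciliation and is minor.

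A reader might infer that the trial plans to test its circulating NET markers before against after and to report recovery as a drug effect. The documents do not support that. The summary speaks of a comparison and names no test, significance level or claim of effect; the link to a drug effect comes from the causal wording of the objective.

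A reader might also infer that such an analysis would usually favour the drug. That goes too far. The lowest rate with 30 pairs is 31%, small bronchial samples give less, and the documents report no natural course for any NET marker. Entry is selected on CRP, not on NETs, so the amount of regression to the mean in NET markers is unknown and their direction of drift is open.

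The low power of 30 against 10 is a fair complaint. It argues for reporting an estimate with its interval, not for dropping the control.

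**Conclusion.** The point holds as an inconsistency with a real consequence. The summary states what will be done with one-arm exploratory data, that analysis cannot answer the exploratory objective, and the SAP does not replace it. It matters where BAC blood samples go unassayed, for bronchial secretions, and for the Day 9, 11 and 14 draws. The size of the bias cannot be computed from the documents: 31-97% (30 pairs) and 8-41% (5-8 pairs) depend wholly on the assumed fall, SD and number of pairs. The primary and secondary results are untouched. Severity is minor.

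**What to change.** Reconcile the Statistical methodology text of the Protocol summary with Protocol 5.1, 11.2.1, 11.3.1 and 11.3.4 and SAP 2.3.3:

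- State that every blood-based exploratory marker will be assayed in both randomised arms at the shared visits, and reported as a baseline-adjusted difference between dornase alfa and randomised BAC with a 95% CI.
- Where control data cannot exist or were not obtained (bronchial secretions, Day 9, 11 and 14 draws under extended dosing), describe the course with the number of patients contributing. Make no before-after test and no claim of drug effect.
- Carry the same rule into whatever document governs the separate exploratory analyses.

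The cost is wording, plus assays on samples already scheduled in about 10 BAC patients. The intervals will be wide at 30 against 10, and the report should say so.
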